**FOOTNOTES FOR APPENDIX IV:**

 Medical history must include pulse, blood pressure, weight and Body Mass Index (BMI) calculated at each visit.

 The initial dose of the HBV vaccination is ideally given at Week 2, though there is flexibility around the timing of the vaccination. Subsequent doses may be given at different visits than indicated in this SOE, as long as sites follow manufacturer guideline timing.

 The HIV testing algorithm is provided in the SSP Manual. If HIV rapid testing is indicated, this testing may be performed in the clinic or the laboratory. At least one HIV assay result must be available and reviewed the same day as sample collection and before product is administered.

 BUN/urea, creatinine, CPK, calcium, phosphorous, glucose, amylase, and lipase.

 AST, ALT, TBili, and alkaline phosphatase.

 Stored plasma will be used for Quality Assurance testing and other assessments at the HPTN LC ([see Section 9](#)) including potential assay for plasma CAB concentrations. Assessments will be performed retrospectively; results will not be returned to

study sites or participants, except as noted in SSP. Samples cannot be used by site or other lab for local purposes without specific instructions from the LC w/ CMC consult. Blood collected for plasma storage must be collected prior to injection.  
 HBsAb and HBcAb will be tested in participants who received the HBV vaccine.

## 12.5 APPENDIX V: SCHEDULE OF ADDITIONAL PROCEDURES FOR REACTIVE/POSITIVE HIV TESTS

(For enrolled participants)

Note 1: The procedures listed for the HIV Confirmation Visit apply to participants who acquire HIV infection at any time during the study. The procedures listed for Weeks 12, 24, 36, and 48 apply to participants who acquire HIV infection after having one or more injections. Participants who acquire HIV in Step 3 may undergo similar procedures as listed in Weeks 12, 24, 36, and 48, and will be determined by the members of the protocol team. Note that participants who acquire HIV-infection during Step 1 will permanently discontinue study product, will be terminated from the study, and be referred for HIV-related care.

Participants who acquire HIV infection in Injection and Follow-up Phase only					
	HIV Confirmation Visit	Week 12	Week 24	Week 36	Week 48
ADMININISTRATIVE, BEHAVIORAL, REGULATORY					
Locator information	X	X	X	X	X
Offer condoms	X	X	X	X	X
HIV counseling	X				
CLINICAL EVALUATIONS AND PROCEDURES					
History, con meds, targeted physical exam	X	X	X	X	X
Blood collection	X	X	X	X	X
LOCAL LABORATORY EVALUATIONS					
HIV testing 	X				
CD4 cell count	X		X		X
HIV viral load testing	X		X		X
HIV resistance testing 	X				
Chemistry testing 		X	X	X	X
Liver function testing 		X	X	X	X
Plasma storage 	X	X	X	X	X
DBS storage	X				

### FOOTNOTES FOR APPENDIX V:

 The HIV confirmatory visit must be held on a different day from the visit where the participant had their initial reactive/positive HIV test. The testing algorithm for the HIV Confirmation Visit is provided in the SSP Manual. If HIV rapid testing is included in the HIV testing algorithm, this testing may be performed in the clinic or the laboratory.

 Sites may collect specimens for resistance testing at a local laboratory to assist with clinical management; results from resistance testing performed at local laboratories will not be reported to the SDMC. Stored plasma may not be used real-time/local resistance testing; additional samples must be collected for this testing.

 Required chemistry testing: BUN/urea, creatinine, CPK, calcium, phosphorous, glucose, amylase, and lipase.

 Required LFTs: AST, ALT, total bilirubin, and alkaline phosphatase.

 Stored plasma will be used for Quality Assurance testing and other assessments at the HPTN LC ([see Section 9](#)), including potential assay for plasma CAB concentrations. Assessments will be performed retrospectively; results will not be returned to study sites or participants, except as noted in Section 9.0. Samples cannot be used by site or other lab for local purposes without specific instructions from the LC w/ CMC consult.

## 12.6 APPENDIX VI: TOXICITY MANAGEMENT

### Toxicity Management General Guidance

In general, the IoR has the discretion to hold study product at any time if she/he feels that continued product use would be harmful to the participant or interfere with treatment deemed clinically necessary according to the judgment of the IoR. In addition, a CMC has been established for this study. The CMC's responsibilities will include consultation and decision-making regarding management of toxicities and study product administration, including product resumption following the occurrence of certain types of toxicities and/or permanent discontinuation. Throughout this appendix are examples of AEs that require consultation with the CMC; in all such cases, the CMC should be notified as soon as possible and ideally within 72 hours of site awareness of the AE in question. IoRs also should consult the CMC for further guidance in restarting study product or progressing to permanent discontinuation.

The following general guidance refers to all AEs except for ALT. Refer to the table below for specific guidance for ALT.

#### **Grade 1 or 2**

In general, participants who develop a Grade 1 or 2 AE regardless of relatedness to study product, and that is not specifically addressed elsewhere in the protocol or in the Tables below may continue use of the study product per protocol.

#### **Grade 3**

For participants who develop a Grade 3 AE or toxicity that is not specifically addressed elsewhere in the protocol or in the Tables below and is judged to be related to study product by the IoR, study product use should be temporarily discontinued in consultation with the CMC. In general, and unless otherwise decided in consultation with the CMC, the IoR should re-evaluate the participant until resolution of the toxicity.

##### **Related:**

For Grade 3 AEs deemed related to study product, the study product should be permanently discontinued if improvement to severity  $\leq$  Grade 2 cannot be documented within 4 weeks of receipt of the initial result. If study product is resumed and the same Grade 3 AE recurs at any time, the IoR must consult the CMC for further guidance on holding of study product, frequency of reevaluation or progression to permanent discontinuation of the study product.

##### **Unrelated:**

For Grade 3 AEs deemed unrelated to study product, the CMC should be consulted for further management recommendations.

#### **Grade 4**

Participants who develop a Grade 4 AE or toxicity that is not specifically addressed elsewhere in the protocol or in the Tables below (regardless of relationship to study product) must have the study product temporarily discontinued. The IoR must consult the CMC and continue the temporary study product hold until a recommendation is obtained from the CMC.

In general, study product use will not be resumed if the Grade 4 AE is considered related to study

product use. If, in consultation with the CMC, study product use is resumed and the same Grade 4 AE recurs at Grade 4 level at any time, study product must then be permanently discontinued.

## **General Criteria for Discontinuation of Study Product**

Participants may voluntarily discontinue the study product for any reason at any time. IoRs will permanently discontinue participants from study product per protocol for any of the specific criteria below, which may be further clarified in the SSP Manual. IoRs also may permanently discontinue participants for reasons not shown here or in the SSP Manual (e.g., to protect participants' safety and/or if participants are unable or unwilling to comply with study product use procedures). In such cases, the IoR or designee must first query the CMC for review. The CMC will provide a written response to the site indicating whether the CMC has recommended permanent discontinuation of study product based on careful review of all relevant data. It should be noted that the safety of the participant should always take precedence, and therefore, an IoR may determine that study product be permanently discontinued before the CMC has time to respond. This is acceptable, and in such cases, the CMC should be notified as soon as possible regarding the nature of the case and the course of action taken.

The criteria for permanent discontinuation of study product use for an individual participant are:

- Study product-related toxicity requiring permanent discontinuation of study product per the guidelines above and below
- Completion of regimen as defined in the protocol
- Request by participant to terminate study product
- Clinical reasons determined by the IoR
- Acquires HIV infection or HBV infection

Study product will be temporarily withheld from a participant for any of the following reasons:

- Report of use of prohibited concomitant medications as described in Protocol Section 4.4. Study product use may resume upon consultation with the CMC and when the participant reports that he is no longer taking the prohibited medication, provided other reasons for temporary study product hold/permanent discontinuation do not apply. The CMC should be consulted in all cases where a participant reports taking a prohibited product during the course of the study.
- The participant is unable or unwilling to comply with required study procedures such as HIV testing and routine laboratory assessments, or otherwise might be put at undue risk to their safety and well-being by continuing study product use, according to the judgment of the IoR. The IoR must consult the CMC on all temporary study product holds instituted for this reason for further guidance on resuming study product use, continuing the temporary hold, or progressing to permanent discontinuation.
- The participant has one or more reactive HIV test results or expresses a concern about having acute HIV infection. Criteria for resuming use of study product in these circumstances are defined in the protocol and SSP Manual.

**Oral Phase:**

Participants who temporarily or permanently discontinue study product during the Step 1, Oral Run-in Phase, will be instructed to return all study products as soon as possible.

**Injection Phase:**

Participants who have received at least one injection and refuse further injections or discontinue due to an AE will be transitioned to quarterly follow-up.

## GUIDANCE ON TOXICITY MANAGEMENT FOR SPECIFIED TOXICITIES:

### Nausea, Vomiting, and Diarrhea

CONDITION AND SEVERITY	IMMEDIATE ACTION	FOLLOW-UP AND MANAGEMENT
Nausea, Vomiting, and Diarrhea		
Grade 1 and 2	Continue study product	Treat symptomatically with hydration, oral antiemetic therapies or antiemetic suppositories at the discretion of the IoR. The IoR should order any clinically relevant laboratory analyses (per judgment of the IoR).
Grade $\geq 3$	Discontinue study product temporarily	Participants with Grade $\geq 3$ nausea, vomiting, or diarrhea, for which an alternative etiology is not established, must discontinue the study product temporarily until Grade 2 or lower and be treated symptomatically. Should condition(s) not improve to Grade $\leq 2$ within 7 days, the IoR should consult the CMC for guidance on continuing the temporary discontinuation or progressing to permanent discontinuation of study product.

## **GUIDANCE ON TOXICITY MANAGEMENT FOR SPECIFIED TOXICITIES:**

### **ALT**

#### **Note for all Grades:**

All study participants will be negative for HBsAg at study entry, and participants who enter the study without evidence of immunity to HBV will be provided HBV vaccination. Therefore, pre-existing HBV infection is not likely to be a cause of AST/ALT elevations.

Careful assessments should be done to rule out the use of alcohol, lactic acidosis syndrome, non-study medication-related product toxicity, herbal medications/supplements, or viral hepatitis as the cause of elevation in AST or ALT of any Grade. The participant must be carefully assessed for any symptoms or signs of hepatotoxicity, including fatigue, malaise, anorexia and nausea, jaundice, acholic stools, right upper quadrant pain, or hepatomegaly. If the AST/ALT elevation is considered most likely to be due to concomitant illness or medication, standard management, including discontinuation of the likely causative agent, if possible, should be undertaken. If symptoms or signs of clinical hepatitis are present, study product must be held or discontinued. In addition, all participants with elevated values should be considered for testing for hepatitis A, B, and C infection.

#### **Note the following for cases of exercise-induced CPK abnormalities:**

Note the following for cases of exercise-induced CPK abnormalities: Cases of CPK abnormality  $\geq$  Grade 3 or higher, presumed to be exercise induced, accompanied by < Grade 3 ALT must be brought to the attention of the CMC for adjudication of further management and further administration of study product. Grades 3 and 4 elevations in ALT, regardless of CK elevation will prompt permanent discontinuation of study product and the participant will be followed annually for HIV testing only until the conclusion of Step 2 of the study. All such cases must be reported to the CMC.

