### **2.3 Study Design and Overview**

We propose a single arm, open label, safety, tolerability, and acceptability study ( $n=$  approximately 50) in sexually-active, healthy adolescents assigned male sex at birth.

Study participation includes, Step 1: a 5-week oral CAB 30mg QD safety lead-in followed by a series of 5 intramuscular (IM) injections of 3 mL (600 mg), administered at 8-week intervals after a 4-week loading dose (injections at weeks 5, 9, 17, 25 & 33) in Step 2. Adherence support strategies (e.g., counseling, reminders, pill cases) will be included to support pill-taking during the first five weeks and to support retention during the injectable phase. A safety visit will follow each injection to ascertain pharmacokinetic-peak safety data, including injection site reactions. Step 3: a blood draw visit, the +8

Week Visit, will follow the last Step 2 injection to monitor CAB drug levels. All participants who have received at least one injection will be followed for 48 weeks after their last Step 2 injection. Waning levels of cabotegravir (the PK tail) will be covered with locally sourced oral Tenofovir/Emtricitabine (Trade name: TDF/FTC, Truvada®) for daily use for 48 weeks or the participant can opt to continue CAB LA injections for the duration of Step 3. Behavioral and acceptability data will be collected via computer-assisted self-interview (CASI).

Participants who discontinue study product during Step 2 for any reason other than HIV infection or AE occurrence will be transitioned to open label Tenofovir/Emtricitabine (Trade name: TDF/FTC, Truvada®) for 48 weeks.

Finally, in-depth qualitative interviews will be conducted after the end of Step 2 (Week 34) with 10 participants (total, across all sites) to explore issues of acceptability and preference for oral tablets and/or injections. Additionally, up to 10 parents/guardians of participants (total, across all sites) will be asked to participate in in-depth interviews to explore facilitators and barriers to adolescent enrollment in biomedical clinical trials as well as parental acceptability of injectable prevention products for youth.

As previously mentioned, we have chosen an unblinded, single arm trial because it is most developmentally-appropriate for adolescents and minimizes participant and staff burden, while also offering a more streamlined visit schedule than the parent protocols and, hopefully, promoting study drug adherence.

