##### Step 3 – Follow-up Phase

All participants who have received at least one injection will be followed for 48 weeks after their last injection, beginning with a blood draw visit, +8 Week Visit, that will follow eight weeks after the last injection to monitor CAB drug levels. Waning levels of cabotegravir (the PK tail) will be covered with locally sourced oral Tenofovir/Emtricitabine (Trade name: TDF/FTC, Truvada®)) for daily use for 48 weeks. Participants will also have the option to remain on CAB LA injections as one 3 mL (600 mg) IM every 8 weeks for 48 weeks, should they choose..

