**Table 5.1. Management of Participants with AEs in Step 1**

Grade of AE	Brief Instruction
Grade 1 AE	Proceed with SOE and to Step 2
Grade 2 AE, excluding ALT	Proceed with SOE and to Step 2
Grade 2 ALT	At Enrollment or Week 2 → continue oral product, repeat ALT labs in 1 week At Week 4 → continue oral CAB, repeat ALT labs in 1 week If result is $\leq$ Grade 1, participant may move to Step 2 if otherwise qualifies;

	If result is $\geq$ Grade 2, permanently discontinue oral CAB, do not move to Step 2 and repeat ALT weekly until $\leq$ Grade 1, then terminate from study
Grade 3 AE, excluding ALT & CPK	Report to CMC and if determined to be: 
 
Related AE <math>\rightarrow</math> permanently stop oral product, follow until stabilizes and then terminate from study
 
NOT related AE <math>\rightarrow</math> follow CMC guidance
 

Grade 3 ALT	Report to CMC  Permanently discontinue oral CAB, do not move to Step 2 and repeat ALT weekly until $\leq$ Grade 1, then terminate from study
Grade 3 CPK + $<$ Grade 3 ALT	Report to CMC for adjudication
Grade 4 AE, excluding ALT & CPK	Report to CMC  Permanently stop oral product, follow until stabilizes and then terminate from study
Grade 4 ALT	Report to CMC  Regardless of CPK permanently stop oral product, repeat ALT labs weekly until $\leq$ Grade 1, then terminate from study
Grade 4 CPK + $<$ Grade 3 ALT	Report to CMC for adjudication

#### 5.4 Transitioning from Step 1 to Step 2

Conditions in Step 1 that could disqualify a participant from transitioning to Step 2 are as follows:

- Pill count suggestive of less than 50% adherence at the Week 4 visit;
- Missed or delayed Week 4 visit;
- Specific AEs per Table 5.1;
- At substantial risk of HIV infection and/or qualifies for oral PrEP by local guidelines;
- Any HIV reactive/positive test (see SSP).

If any of the above conditions occur, investigators should notify the HPTN 083-01 CMC at [contact] within one week of awareness for final determination of fitness to enter Step 2.

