#### **5.7 Step 3, Follow-up Phase**

##### **Follow-up Phase**

All participants will be followed for 48 weeks following their last injection in Step 2 (per [Appendix III and IV](#)) and will have the choice of continuing on CAB LA or being provided with Tenofovir/Emtricitabine (Trade Name: TDF/FTC, Truvada®). If participants would like to switch from TDF/FTC to CAB LA in Step 3, that is allowable, but it will not lengthen Step 3.

Step 3 will begin with the +8 Week Visit, in which participants who received the Week 33 injection will return for a blood draw eight weeks afterwards, in order to complete PK monitoring of drug levels of CAB. Participants who do not receive the week 33 injection will have a +8 Week Visit after their last injection visit and continue to be followed per the Step 3 Follow-up Phase.

Both clinical and laboratory evaluations will occur during follow-up phase visits as well as CASI administration for either behavioral or acceptability assessments (see [Appendices III. and IV.: Schedule of Evaluations for Follow-up Phase – Step 3-Oral PrEP and Step 3-Injection](#)).

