## GUIDANCE ON TOXICITY MANAGEMENT FOR SPECIFIED TOXICITIES:

CONDITION AND SEVERITY	FOLLOW-UP AND MANAGEMENT
ELEVATIONS in ALT	
Grade 2 and higher – Oral Phase	
Oral phase: A Grade 2 ALT abnormality reported at Week 2 or Week 4, regardless of relatedness to the study product, should be confirmed within one week. Oral study drug may continue until the confirmatory results are available; no injections should be administered until confirmatory results are available during consideration of the Week 4 ALT value. If the repeat value is <math>\leq</math> Grade 2 at Week 3, study drug may continue to Week 4. If the repeat value is <math><</math> Grade 2 at Week 4, the participant may proceed to the injection phase. If the repeat value is Grade 2 or higher at Week 4, study product should be stopped, and the participant will be discontinued from the study. All such cases must be reported to the CMC. In addition, participants will be followed with weekly ALT assessments until they return to <math>\leq</math> Grade 1.

Grade 3 and higher – Oral Phase	
Oral Phase: A Grade 3 or higher ALT abnormality, regardless of relatedness to the study product, will result in permanent study product discontinuation and will prohibit a participant from entering the injection phase of the study. All such cases must be reported to the CMC. In addition, participants will be followed with weekly ALT assessments until they return to <math>\leq</math> Grade 1.

CONDITION AND SEVERITY	FOLLOW-UP AND MANAGEMENT
ELEVATIONS in ALT	
Grade 2 and higher – Injection Phase	
Injection phase: The CMC should be notified as soon as possible.
 
For a Grade 2 ALT, the CMC will determine whether further injections may be given in cases where levels are <math>\leq</math> Grade 2 prior to the next scheduled injection. Unless otherwise specified by the CMC, for Grade 2 ALT, repeat testing should be performed weekly until levels are <math>\leq</math> Grade 1.

Grade 3 and higher – Injection Phase	
Injection Phase: For Grade 3 and higher ALT, study product will be permanently discontinued. For Grade 3 and 4 ALT, repeat testing should be performed as soon as possible, and participants should be followed weekly until levels are <math>\leq</math> Grade 1. Participants who are permanently discontinued from study product should continue to be followed 48 weeks post-last injection.

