## GUIDANCE ON TOXICITY MANAGEMENT FOR SPECIFIED TOXICITIES:

### Creatine Phosphokinase (CPK)

#### Note the following for cases of exercise-induced CPK abnormalities:

Note the following for cases of exercise-induced CPK abnormalities: Cases of CPK abnormality  $\geq$  Grade 3 or higher, presumed to be exercise induced, accompanied by < Grade 3 ALT must be brought to the attention of the CMC for adjudication of further management and further administration of study product. Grades 3 and 4 elevations in ALT, regardless of CK elevation will prompt permanent discontinuation of study product and the participant will be followed for 48 weeks post-last injection. All such cases must be reported to the CMC.

CONDITION AND SEVERITY	IMMEDIATE ACTION	FOLLOW-UP AND MANAGEMENT
Creatine Phosphokinase		
Grade 3	Continue study product until repeat test results are available	A Grade 3 or higher elevation in CPK should result in a repeat assessment within 2-4 weeks to ensure the result is transient or due to exercise and will not require a change in study treatment. A history regarding use of products known to cause increase of CPK (such as statins), physical activity, or exercise preceding the CPK evaluation should be obtained.
Grade 4	Continue study product until repeat test results are available if the elevation is thought to be possibly or probably related to study product.	Grade 4 elevations in CPK should have a repeat assessment after the subject has abstained from exercise for >24 hours. For persistent Grade 4 CPK elevations that are considered possibly or probably related to the study product, study product should be discontinued and the participant should be followed on study/off study product.

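### The follow-up clause for Grade 3–4 ALT in the ALT section of Appendix VI contradicts the ALT table, the matching CPK note and the 48-week rule (minor, low likelihood)

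*Protocol*

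**What the plan says.** Appendix VI prints a note on exercise-induced CPK abnormalities twice, once in the ALT section and once in the CPK section. Both versions stop product permanently for Grade 3 and 4 ALT irrespective of CK, so the sentence reaches every such ALT and not only exercise-related cases. They differ in what follows:

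- ALT section: "the participant will be followed annually for HIV testing only until the conclusion of Step 2 of the study".
- CPK section: "the participant will be followed for 48 weeks post-last injection".

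The injection-phase row of the ALT table, for Grade 3 and higher, asks for weekly repeat testing until Grade 1 or lower and adds: "Participants who are permanently discontinued from study product should continue to be followed 48 weeks post-last injection". The Injection Phase paragraph of Appendix VI moves injected participants who stop because of an adverse event to quarterly follow-up.

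The general rule is stated in several places. Section 2.3: "All participants who have received at least one injection will be followed for 48 weeks after their last Step 2 injection". Section 5.7: "All participants will be followed for 48 weeks following their last injection in Step 2". Section 4.1 has those injected "followed for 48 weeks after their last injection, beginning with a blood draw visit". The Schema and Section 7.1 also give 48 weeks.

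Step 1 has its own rule. For Grade 3 ALT, Table 5.1 stops oral CAB, bars entry to Step 2 and repeats ALT weekly until Grade 1 or lower, after which the participant is terminated from the study. Grade 4 ALT is handled in the same way.

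**The concern.** A Grade 3 or 4 ALT is among the most serious laboratory events this protocol plans for, and it ends dosing with a depot that cannot be removed (Section 1.10). One sentence in the ALT section then replaces laboratory follow-up with an annual HIV test that stops when Step 2 stops. A site that applied it would drop scheduled liver monitoring and quarterly HIV testing while cabotegravir may still be present. In adult men in HPTN 077 the median time to undetectable drug was 42.7 weeks (Section 1.5.2).

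The data at stake are recovery of the liver event, its peak severity and later events. Safety over the 48 weeks after the final injection is a secondary objective (Section 2.2), and the protocol's primary safety analysis runs to the same point (Section 7.7.1).

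**Working it through.** **1. The plan's own figure.** Section 2.3.2 gives a total commitment of about 82 weeks: 5 (oral) + 29 (injection) + 48 (follow-up) = 82. This is reproduced, and it relies on the 48-week follow-up. Counted from the Week 33 injection itself, the end is 33 + 48 = Week 81.

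**2. The rules side by side, for Grade 3–4 ALT in an injected participant.**

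| Place | Frequency and content | End |
|---|---|---|
| Appendix VI, ALT section, CPK note | annual, HIV test | end of Step 2 |
| Appendix VI, ALT table, injection-phase row | ALT weekly until Grade 1 or lower | 48 weeks after last injection |
| Appendix VI, CPK section, same note | not stated | 48 weeks after last injection |
| Appendix VI, Injection Phase paragraph | quarterly | not stated |
| Schema, Sections 2.3, 4.1, 5.7, 7.1 | Step 3 schedule | 48 weeks after last (or last Step 2) injection |

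The word *only* in the clause can attach to HIV testing or to the end date. Either way the clause conflicts with the ALT table and with the CPK-section note.

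**3. Can an annual visit occur?** Injections are at Weeks 5, 9, 17, 25 and 33, and Step 2 ends with the Week 34 safety visit. The longest interval from any injection to the end of the participant's own Step 2 is 34 − 5 = 29 weeks, which is less than 52. An annual visit counted from an injection, or from a later ALT event, therefore never falls due. Counted from enrolment it would fall at Week 52, also after Week 34.

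**4. Loss if follow-up ends with Step 2, last injection at Week 33.**

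- End under the 48-week rule: 33 + 48 = Week 81.
- End under the clause: Week 34.
- Difference: 81 − 34 = 47 weeks.
- Appendix III visits with both a liver panel and an HIV test are +12, +24, +36 and +48, that is Weeks 45, 57, 69 and 81. All four come after Week 34, so four liver panels and four HIV tests would be lost.

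**5. SAP endpoints.** The primary safety window closes 8 weeks after the last Step 2 injection visit or at Week 41, whichever is first (SAP 8.1). The secondary Grade 2 or higher analyses end at Week 5, 8 weeks after the last injection received, or about 36 weeks after the first injection (SAP 12.2, 12.3). A participant with Grade 3–4 ALT inside a window already counts as having a Grade 2 or higher event, so shorter follow-up does not alter that binary result.

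**The case against.** The strongest reply is that the intended rule can be recovered. The general guidance in Appendix VI sends the reader to the table for ALT, and the table is explicit. The Injection Phase paragraph gives quarterly follow-up, and Section 6.1 requires clinical follow-up until an event resolves or stabilises. The note itself requires every such case to be reported to the CMC. SAP 6.4 records that enrolment stopped at nine participants. On this view the clause is a leftover in a note about exercise and CPK. That argument stands as to likelihood and holds the rating at minor. It does not make the clause correct, and a site working through the ALT section meets it before the table.

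A reader might infer more than the documents support:

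- **That liver panels fall to zero on every reading.** The clause does not terminate the participant, whereas Table 5.1 says so when that is meant. If the clause governs only the period up to the end of Step 2, Section 5.7 and Appendix III apply afterwards, and all four liver panels and HIV tests in step 4 of the working remain.
- **That participants who stop earlier lose a fixed number of weeks, counted to Week 34.** Section 5.7 and the lipid footnote to Appendix II move early discontinuers into Step 3, so their own Step 2 ends before Week 34. No such figure is fixed.
- **That the size can be computed with Step 2 taken study-wide, or for ALT events after Step 3 injections.** The first depends on planned recruitment times that were not realised. The second depends on which visit schedule applies once Step 3 injections stop, which the documents do not say.
- **That the 48 weeks should be tied to the last Step 2 injection in both notes.** The ALT table has no such limit. After a Step 3 injection at +40 this anchor would leave 8 weeks of scheduled follow-up (48 − 40), and after one at +48 none. The Section 5.7 remark, "that is allowable, but it will not lengthen Step 3", concerns a voluntary switch from TDF/FTC to CAB LA, not follow-up after a liver event.

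The mismatch with Step 1 is real but adds little, since Table 5.1, Section 5.4.1 and the oral-phase ALT rows already govern those cases.

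**Conclusion.** The contradiction is real, lies in current text and needs no outside source. It is minor, with a low likelihood of harm. For injected participants with Grade 3–4 ALT, the ALT-section clause disagrees with the injection-phase ALT row, the matching CPK note, the quarterly rule and the general 48-week rule. Within a participant's own Step 2 it also sets an annual visit that cannot occur.

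The size is at most 47 weeks of follow-up, four liver panels and four HIV tests. That figure assumes a last injection at Week 33, Step 2 taken as the participant's own and ending at Week 34, and the clause read as ending follow-up there. On the reading that limits the clause to Step 2, that participant loses none of those visits. No SAP endpoint changes. What could be lost is information on resolution, severity and later events in the 48 weeks after injection.

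**What to change.** In the CPK note within the ALT section of Appendix VI, replace the follow-up clause with:

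*participants who have received at least one injection will have ALT repeated weekly until Grade 1 or lower and will be followed quarterly for 48 weeks post-last injection; Step 1 cases follow Table 5.1.*

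This brings the note into line with the ALT table, the CPK-section note and the Injection Phase paragraph. Do not tie follow-up to the last Step 2 injection in either note. The cost is one clause in a clarification memo to the sites. No SAP change is needed.
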